#### Section 2 - Research Sites and Sponsor

5. Please list all Research Sites in addition to Louis Stokes Cleveland DVA Medical Center (LSCDVAMC); NA

International studies when the PI is the Lead Investigator list the countries:

a. When study procedures including analysis of identifiable samples or data involving LSCDVAMC enrolled subjects will be conducted at any site other than the LSCDVAMC please provide the following:

Name and contact information for the site:

Describe the plan for communicating protocol amendments, reports of serious adverse events, reports of unanticipated problems involving risks to subjects or others, interim reports, and DSMB reports to external sites.

- \* When the LSCDVAMC is considered the coordinating center and the PI the lead investigator on cooperative research or a multi-center trial contact AO/Research [contact].
- **6. Sponsor or other Support** (list industry sponsor, government support, etc.): Department of Defense

### Section 3 – Research Design and Procedures

7. Definitions- Provide a list of all abbreviations and specialized terms to be used in this document and their definitions:

Abbreviations / Specialized Terms (Use the Enter key in this column to insert additional abbreviations and their definitions)	Definition
LSCDVAMC	Louis Stokes Cleveland DVA Medical Center
DOD	Department of Defense
TBI	Traumatic Brain Injury
ADL	Activities of Daily Living
TMS	Transcranial Magnetic Stimulation
fMRI	functional Magnetic Resonance Imaging
FES	Functional Electrical Stimulation
ROM	Range of motion
BBT	Box and Blocks Test
CAHAI	Chedoke Arm and Hand Activity Inventory
OPUS-UEFS	Orthotic and Prosthetic Users' Survery upper extremity functional status

Abbreviations / Specialized Terms (Use the Enter key in this column to insert additional abbreviations and their definitions)	Definition
OPUS-Sat	Orthotic and Prosthetic Users' survey of satisfaction
CHART	Craig Handicap Assessment and Reporting Technique
MMT	Manual muscle testing
EMG	Electromyography
iSP	Ipsilateral Silent Period
MEP-rc	Motor evoked potential recruitment curve
SO	Stimulator Output

- **8.** Provide a BRIEF SUMMARY of the background for this research. DO NOT CUT and PASTE paragraphs that do NOT summarize the background.
  - Include a critical evaluation of existing knowledge, and specifically identify the information gaps that your protocol is intended to fill.
  - Refer to appropriate citations in the scientific literature and include your references at the end of this section.
  - *Include the rationale for conducting the research at the VA.*

TBI affects 1.7 million people in the general population [1] and is one of the most common neurologic disorders causing disability [2]. The estimated direct and indirect cost for TBI is \$76.5 billion in the US and motor deficits are present in 30% of TBI survivors [3]. TBI is also a major challenge in the military and Veteran populations. Since 2000 to June 2015, there have been 36,000 moderate and severe TBI incidents among U.S. military and civilian casualties in the active missions Operation Freedom's Sentinel (OFS, Afghanistan) and Operation Inherent Resolve (OIR, Iraq and Syria) and, as well as operations that have ended, Operation New Dawn (OND, Iraq), Operation Iraqi Freedom (OIF, Iraq), and Operation Enduring Freedom (OEF, Afghanistan) [4]. These numbers represent medical diagnoses of TBI that occurred anywhere US forces are located, including the continental US.

Research on motor recovery in patients with TBI is scarce compared with other neurologic diseases involving the brain, such as stroke [2]. Specifically, arm and hand paresis occurs in approximately 17% of TBI patients [5] and may limit an individual's ability to undertake activities of daily living (ADL). The recovery time of upper extremity weakness is different according to the mechanism of injury (patients with diffuse brain injury recover more slowly than those with focal injury), severity of initial weakness, and time spent unconscious [2]. Compared to stroke, motor recovery in patients with TBI is characterized by a low incidence, decreased severity, and good prognosis [2]. However, inspite of the difference in trajectory of recovery in early stages after stroke and TBI, there are similarities in the course of disease in chronic stages. In both conditions, motor defcitis are caused by injury to the corticospinal tracts or motor control centers in the brain. Furthermore, there is significant overlap in therapeutic approches for motor restoration [43]. Therefore, therapies tested in stroke population can be successfully applied in treatment for patients with TBI.

Multi-disciplinary rehabilitation has been shown to improve the experience of living with a long term neurological condition. Although we now understand that brain plasticity plays a

significant role and offers a window of opportunity to promote recovery, we still do not know how to maximize recovery [6]. Activity-based interventions hope to maximize neural plasticity [3], however, optimal doses and schedules of training have not been adequately established. Repetition is one parameter important for experience-dependent neural plasticity. Studies assessing US rehabilitation found that stroke and TBI survivors receive an average of 32–50 repetitions of upper extremity active and passive movement per therapy session, less than the 400-600 repetitions used in animal studies [3]. Although TBI survivors benefit from traditional therapy, it is clear that more is needed to attain full recovery, especially with severely affected individuals. Hence, various technologies to supplement therapy are being investigated, including robotic therapy.

Advances in technology have led to development of a variety of robotic devices for rehabilitation of the impaired upper limb. Robotic therapy can manipulate different practice variables, including intensity, repetition and specificity [3]. Robotic technologies have been shown to efficiently provide intense task oriented therapy within a structured program [7] with comparable results to conventional therapy in improving motor impairment, activity and participation [8-12]. However, only wearable devices allow therapy with the impaired limb to be undertaken anywhere from bedside to home, potentially providing both a therapeutic effect as well as everyday functional assistance. From a therapeutic perspective, it has been proposed that facilitating the ability to practice tasks repetitively forms new neural connections in the brain and reinforces existing connections, resulting in improved ability to move the arm [13]. Functionally, this allows a person with an upper limb impairment to perform ADLs such as feeding, reaching, and lifting with the assistance of an orthosis. When asked which feature of upper limb robotics they liked the most, therapists stated that they liked that most robotic devices allow individuals with upper limb neurological impairment to do more repetitive practice on their own [14]. Further, the therapists felt that by doing more volitional movement on their own (or aided by the device in some cases), individuals with neurological impairment get more intrinsic input; this could potentially lead to greater improvements in motor performance over time [14]. Best practices for integrating robotic devices within an upper limb intervention program can only be derived through widespread collection of data [14].

Krebs and Volpe [6] argued that the basis of all assistive and therapeutic devices should be to determine intent to move followed by that movement actually happening, referred to as "intent-driven rehabilitation". This can be accomplished through myoelectric control wherein the trace electrical activity volitionally generated by contracting muscle in an impaired limb is amplified, processed, and used to control the flow of electricity from a battery to a motor, which operates an orthosis. The patient-directed "intentional" action of the device promotes patient engagement as the orthosis will only reward the patient with movement when they use the correct muscles to complete a task. Previous myoelectric driven, lab-based robotic interventions [15] have been shown to improve Fugl-Meyer motor control scores of the upper extremity [16] and reduce spasticity as assessed by the Modified Ashworth Scale (MAS) [17]. While a few one-off wearable myoelectric upper limb orthoses have been described [18-20], the only commercially available, wearable, myoelectric upper limb orthosis is the MyoPro from our collaborators at Myomo Inc., Cambridge MA (brochure in appendix).

Wearable myoelectric orthotic technology was developed in 2006 at Massachusetts Institute of Technology (MIT) and subsequently commercialized by Myomo Inc. as the e100 System in 2007 [6, 13, 14, 21-23] and updated as the mPower 1000 System in 2012 [24-28]. These initial designs enabled individuals to initiate and control only elbow motion and were used to facilitate therapy [23, 25]: individuals with decreased motor control, coordination and/or

strength use the biofeedback provided by the device to practice activation and inhibition of the biceps and triceps muscles [26]. In 2012, Myomo introduced the MyoPro custom fit powered elbow orthosis designed for home use to facilitate functional tasks and patient independence.

While Myomo reports that they currently have 16 MyoPro users with TBI, initial research publications have focused on persons with stroke [22, 23, 25-29]. The ability of severely hemiplegic stroke survivors to activate a powered elbow orthosis using myoelectric control has been reported [23], along with increased elbow range of motion with device use [29]. The feasibility of combined clinic and home use in persons post-stroke [26] has also been demonstrated. Kim et al. [26] reported that after a combined period of training and at home use of the elbow-only MyoPro device, a statistically significant 3 point change in Fugl-Meyer motor control score was found in the upper extremity of 9 persons post-stroke. This positive change occurred despite study limitations: including limited therapy (chronic post-stroke subjects received training on how to don/doff and use the device but no additional therapy) and low usage rates (had home use of less than one hour per day). Combining device training with motor therapy and encouraging greater at home use may result in further improvements. It is an unfortunate reality of clinical practice where resources are limited that persons with static central nervous system (CNS) injuries such as stroke and TBI do not continue to get therapy despite research suggesting that improvements in motor control can be made even when the conditions are chronic. Ongoing use of myoelectric devices may help to address this gap in patient care.

Goals of device use identified anecdotally by current MyoPro users are similar to those identified by people with impairments using rehabilitation robotics [30]. They include improving overall arm movement for the purpose of performing functional tasks such as feeding and drinking, lifting and carrying objects, operating light switches, cooking, dressing, and using a cell phone. However, the MyoPro has until now been limited to training/assisting a single degree of freedom at the elbow [21, 26] and enhanced device functionality is needed to help accomplish some of the goals patient's desire. Hence, Myomo recently combined the powered elbow with powered grasp in the new MyoPro Motion-G orthosis. Given the goals that patients report, it is anticipated that with the addition of the hand component, which allows a three point chuck grasp, there will be an increase in patient functionality and independence when used to augment therapy. However, the benefits of adding powered grasp in conjunction with elbow function are unknown.

Similar to the use of Functional Electrical Stimulation (FES), use of myoelectric orthoses may be considered to have both a therapeutic and orthotic effect [31]. Therapeutic effect refers to improvements in impairment. Impairment is defined by the International Classification of Functioning, Disability and Health (ICF) framework as "problems in body function and structure" [32]. In our case these include reduced active or passive upper limb range of motion and motor performance that carryover outside of orthosis use. Orthotic effect refers to the functional improvements that are possible while wearing the orthosis that increase activity and participation. Activity and participation are defined by the ICF as "execution of a task or action" and "involvement in life situations", respectively [32]. The basis for a therapeutic benefit of intent-triggered myoelectric devices likely rests in the reinforcement of volitional muscle control [6] and the ability to gradually progress training wherein the electromyography (EMG) signal activation threshold to trigger mechanical motion can be gradually increased. Thus, myoelectric orthoses provide the opportunity to engage and build on small residual volitional muscle activation in individuals with upper limb motor impairment due to TBI.

Wearable myoelectric orthotic technology was developed in 2006 at Massachusetts Institute of Technology (MIT) and subsequently commercialized by Myomo Inc. as the e100 System in 2007[6, 21-23] and updated as the mPower 1000 System in 2012[24-27]. These initial designs enabled individuals to initiate and control only elbow motion and were used to facilitate therapy[23]: individuals with decreased motor control, coordination and/or strength use the biofeedback provided by the device to practice activation and inhibition of the biceps and triceps muscles[25]. In 2012, Myomo introduced the MyoPro custom fit powered elbow orthosis designed for home use to facilitate functional tasks and patient independence. In 2015, the Myomo added a hand/wrist component to the orthotic device enabling grasping function.

Furthermore, brain plasticity as it occurs in the TBI population has not been well studied[33], and many questions remain regarding how activity dependent use of the paretic limb leads to structural and functional reorganization of the brain after TBI[33]. Though a few studies can be found that demonstrate neuroplasticity in response to intervention for chronic TBI[34,35], no studies measuring actual cortical change in response to upper limb intervention were identified. Emerging, non-invasive methods for measurement of neuroplasticity have the capability of detecting changes in response to treatment. These measures include Magnetic Resonance Imaging (MRI) based methods and Transcranial Magnetic Stimulation (TMS) techniques. MRI-based techniques include resting state functional MRI and Diffusion Tensor Imaging and evaluate functional and structural changes in the whole brain. Using TMS, we can assess neurophysiological changes in the motor system and interactions between different brain regions. We will also obtain electromyogram – based measure of corticospinal function called H-reflex.

In summary, upper limb motor deficits in TBI are a problem that can lead to decreased independence in ADLs. In particular, there is a lack of effective ongoing therapies and supportive devices for upper limb impairment. However, a potentially powerful tool has just emerged in the form of the MyoPro Motion-G orthosis but the benefits are as yet unexplored.

#### 10. Describe the means of analyzing the data and evaluating the results.

- State the anticipated methods to be used for analysis and interpretation of the data.
- The methods must compliment the design of the study and the nature of the data which is being collected.

As a primary analysis of therapeutic benefit, we will use a paired t-test to compare the difference between baseline and final evaluation at the end of the home use period. A similar comparison using the Box and Block Test results will be used as the primary analysis of functional benefit. For these primary analyses, critical alpha will be adjusted using the Bonferroni correction to account for Type 1 error.

Secondary analyses will assess changes over time in each outcome measure as well as correlations between satisfaction and measures of motor impairment and function (both perceived and actual). We anticipate that the therapeutic measures will increase initially before plateauing while functional measures are expected to increase slowly at first with

continued gains across the home use period. We expect that satisfaction will be positively correlated with perceived improvements in function.

We will use single subject analysis to evaluate changes over time for each outcome measure. In order to capture individual effects, baseline to end of home use outcomes data will be plotted, with outcome measure score on the vertical axis and time/transition through conditions (therapy/training to home use) on the horizontal axis. Visual inspection in the form of change in trend (i.e., a systematic variation in the slope of the data points from one phase to the next) will be used. [name] has some experience with single subject analyses as detailed in a paper accepted for publication that evaluated ankle foot orthoses effect on community ambulation outcomes in children with cerebral palsy.

Spearman's correlation will be used to assess the relationship between OPUS satisfaction with device and Fugl-Meyer Assessment of Motor Recovery upper limb subsection score, as well as OPUS satisfaction with device and OPUS functional status.

As a primary analysis of MRI-based measures, we will use a paired comparison between baseline and post training evaluation (prior to home use period). For the TMS-based measures, we will compare data between baseline, at week 9, after the end of the therapy and after the end of the home-use phase. We will evaluate changes over time for each outcome measure.

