## 11. Provide a BRIEF DESCRIPTION of how the estimated number of study subjects needed for this research was determined

- If this is a quantitative study provide the method of determining sample size estimates.
- If multiple studies are planned provide a power analysis or justification for each one.

To determine our sample size, we utilized data obtained from a previous pilot study [26]. In that study of 9 patients with stroke, a change in the Fugl-Meyer Assessment of Motor Recovery upper limb subsection score of  $3.2 \pm 2.91$  was reported to be statistically significant [26]. This data was used to calculate effect size (d = 1.107) because we do not have pilot data for TBI. Using the G\*Power computer program [53] this effect size was used to estimate sample size. For a 1-tailed matched pairs t-test (comparing baseline to final evaluation at end of home use period) we would need a total sample size of 11 to detect an effect size of 1.107 with a critical alpha of 0.05 and power of 0.95. In order to account for possible attrition in subject numbers we will recruit 20 persons with TBI or stroke. Furthermore, we estimated that we would need to screen 70 subjects to recruit 20.

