- Safely and correctly performs all the given tasks
- Adjust the device to the correct settings for each task
- Independently performed the home treatment program at least one time
- Understands all safety precautions associated with device usage during activities

Study Part 4 – Home Use: Having demonstrated the above competencies, subjects will start a 9-week program practicing upper limb activities at home. Subjects will have reassessments in the clinic as needed to trouble-shoot any technical issues, monitor adverse events, and/or upgrade their home program. Every third week, there will be one session at the clinic for outcomes evaluation. The subject will record daily at home use of the device in a paper calendar log.

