#### OUTCOME MEASURES for each AIM:

Aim 1: Evaluate therapeutic and neuroplastic effects of myoelectric upper limb orthosis

When assessing robot- or orthosis-assisted functional tasks, no one measure is perfectly applicable [34], hence we will use a combination of outcome measures. To evaluate the therapeutic effect of the myoelectric upper limb orthosis with powered elbow and grasp, outcome measures will include range of motion, MAS, the Wrist Position Sense Test, monofilament test of sensation, and the Fugl-Meyer Assessment of Motor Recovery upper limb subsection. These measures will be performed without the orthosis to assess whether therapy/training combined with device usage result in carry-over effects at the body structure level over time. See Table 2 for overview of schedule of assessments.

Passive range of motion is the amount of motion of a joint measured in degrees by a clinician with a goniometer during a passive movement. Passive range of motion of the elbow and fingers will be assessed.

The MAS will be used to assess muscle tone and spasticity [17]. Using a 5 point scale, the clinician evaluates resistance to passive movement about a joint with varying degrees of velocity. The MAS has been widely used to quantify muscle tone following brain injury. Interrater reliability of MAS for arm assessments has been reported as kappa=0.92 or percent of agreement = 97.4% [35].

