Ipsilateral silent period (iSP). In order to evaluate transcallosal inhibition, we will analyze the iSP in the flexor dorsal interosseous muscle. An iSP in the affected limb is elicited by stimulating the M1 hotspot of the unaffected muscle while the paretic muscle is active. The reduction in muscle activity due to the ipsilateral stimulation is analyzed. Suprathreshold TMS is applied at 150% of the unaffected muscle's rMT (or at 100% SO, in the event of high rMT) while the subject activates their affected muscle at 20% of their maximum voluntary contraction level, monitored with visual feedback of the EMG recording. The EMG data from 10 stimuli are recorded, averaged and rectified. The iSP onset and offset are determined by analyzing the averaged, rectified data relative to a threshold determined by the pre-stimulus mean EMG value. iSP onset is defined as when the EMG falls below the threshold, and iSP offset is when the EMG returns to within 25% of the threshold for at least 50 ms[62]. We will compute both duration and the amount of EMG suppression during iSP.

Aim 2: Evaluate functional effects of myoelectric upper limb orthosis

To evaluate the functional effect of the myoelectric upper limb orthosis with powered elbow and grasp, outcome measures will include performance-based measures such as the Box and Block Test (BBT) and the Chedoke Arm and Hand Activity Inventory (CAHAI). The performance-based measures will be performed both with and without the orthosis to assess whether device usage improves function at the level of activity over time. During the period of home use, patient reported measures such as the Orthotic and Prosthetic Users' Survey (OPUS) upper extremity functional status (OPUS-UEFS) and satisfaction with device (OPUS-Sat) as well as the Revised Craig Handicap Assessment and Reporting Technique (CHART) to assess life-role participation and level of community integration will be added. The patient-reported measures will be completed to assess whether device usage at home improves perception of function and participation over time. See Table 2 for overview of schedule of assessments.

The Box and Block Test (BBT) is a standardized assessment of unilateral gross manual dexterity.

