# 40. Describe all procedures that minimize risks, please include study and standard of care procedures:

# Procedures that minimize Potential Foreseeable Risks-orthosis and study treatment/testing procedures

- The total duration of the study is about 31 visits over a period 22 weeks, which is a long commitment and increases risk of subject dropout. Subjects are informed of their time commitment during the screening phase and at enrollment consent and throughout their study participation.
- There is a possibility that some discomfort may arise while wearing the orthosis. Subjects will be required to wear the device for up to two hours during training and as long as tolerated at home. If at any time they feel uncomfortable, they are instructed to inform the researchers so that modifications can be made to the orthosis to improve comfort.
- There is a possibility that if the subject had ever experienced issues with shoulder instability or pain using the orthosis may cause these issues to flare up again Shoulder stability and pain will be monitored throughout the study to ensure that the device is not causing problems. Development of shoulder pain or additional subluxation during the course of the study would result in subject withdrawal from the study if modifications such as adding a shoulder harness were insufficient to overcome shoulder stability issues.
- The manufacturers of the orthosis have been careful to ensure that it is safe and cannot apply a dangerous amount of force to the arm or hand. Safety mechanisms have been implemented into the control software, the electronics hardware, and the mechanical hardware of the brace. For example, in the software commands that control the orthosis and the electronics of the orthosis, there are limits on the amount of force that can be commanded to the system. The mechanical system contains physical limits that prevent the orthosis from exerting force in an unsafe direction. In the worst case scenario, if all of these safety mechanisms fail, there is a small risk that the arm could be injured.

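### Both primary tests use only the week-1 and week-22 scores with no missing-data rule, so a subject without week 22 drops out of both, although earlier scores that could protect the estimate are already scheduled

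*Combined protocol and SAP*

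**What the plan says.** Item 10 sets the primary therapeutic analysis: "As a primary analysis of therapeutic benefit, we will use a paired t-test to compare the difference between baseline and final evaluation", the final evaluation being at the end of home use (week 22 in Table 2). For function, "A similar comparison using the Box and Block Test results will be used as the primary analysis of functional benefit". Both carry a Bonferroni adjustment. Scores from other visits enter only secondary analyses of change over time and single-subject plots read by eye. Item 10 also expects that "therapeutic measures will increase initially before plateauing while functional measures are expected to increase slowly at first".

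Table 2 in Item 13 schedules Fugl-Meyer without the orthosis at weeks 1, 5, 7, 9, 13, 16, 19 and 22 (eight scores) and BBT without it at weeks 1, 5, 9, 13, 16, 19 and 22 (seven). On the Aim 1 therapeutic measures the plan says "These measures will be performed without the orthosis to assess whether" gains carry over. For Aim 2, "The performance-based measures will be performed both with and without the orthosis", although at week 1 the BBT is done only without it.

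On attrition, Item 11 computes 11 subjects and adds: "In order to account for possible attrition in subject numbers we will recruit 20 persons with TBI or stroke". Item 40 says of the 31 visits, "which is a long commitment and increases risk of subject dropout". Entry to the last phase is conditional: "Having demonstrated the above competencies, subjects will start a 9-week program practicing upper limb activities at home". No missing-data rule, imputation method or analysis set is stated, and Item 14 records no control group.

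**The concern.** A paired t-test needs both scores. A subject seen up to week 19 has seven no-orthosis Fugl-Meyer scores and still contributes nothing to the primary test. Recruiting 20 against 11 protects power, but not against selective loss. With no control arm there is no second group in which the same selection could partly cancel, so if poorer responders leave more often, the completers' mean change rises and the rise reads directly as benefit.

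**Working it through.** **Readings needed.** Item 10 does not name the therapeutic measure; I read it as Fugl-Meyer because Item 11 sizes the comparison on it. Item 10 gives neither sidedness nor the adjusted alpha; I use one-sided 0.05/2 = 0.025, from the 1-tailed test in Item 11 and Bonferroni for two tests.

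**The plan's own figure.** Power = 1 − F(t(1−α, n−1)), with F the noncentral t distribution on n−1 df and noncentrality d√n. With d = 1.107 and one-sided α = 0.05, n = 10 gives 0.943 and n = 11 gives 0.961, so 11 is reproduced. (3.2/2.91 is 1.0997, not 1.107; this also gives 11.)

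**Power after random loss.** With d = 3.2/2.91 and one-sided 0.025: 11 pairs 0.907, 12 pairs 0.933, 13 pairs 0.953, 20 pairs 0.997. Seven of 20 can be lost before power falls below 0.95, so power is not the main issue.

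**Bias if loss follows earlier change.** From the plan: 20 enrolled and SD of change 2.91. Assumed: true mean change 0; measurement SD σ = 1.2 or 1.7; loss just after week 13 with weight exp(−kz), where z is the standardised observed week-13 change; individual change linear, flat after week 13, or exponential with a 6-week constant; normal scores.

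True-change variance is τ² = 2.91² − 2σ², which is 5.588 at σ = 1.2. Let f be the share of the week-22 change reached by week 13, x the week-13 change and y the week-22 change. Then Var(x) = f²τ² + 2σ², Cov(x, y) = fτ² + σ², and

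completer bias = [Cov(x, y)/Var(x)] × (mean x in completers − mean x in all).

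- Flat after week 13 (f = 1), σ = 1.2: Var(x) = 5.588 + 2.880 = 8.468 (SD 2.91), Cov = 5.588 + 1.440 = 7.028, slope 0.830. With k = 1 and 7 lost, simulated bias was 0.82, so completers sit 0.82/0.830 = 0.99 points, or 0.34 SD, above the whole group at week 13.
- Linear (f = 12/21 = 0.571), σ = 1.2: Var(x) = 1.825 + 2.880 = 4.705 (SD 2.169), Cov = 3.193 + 1.440 = 4.633, slope 0.985. The same 0.34 SD shift predicts 0.985 × 0.34 × 2.169 = 0.73; the simulation gave 0.72.

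Simulated ranges over the three shapes and both σ:

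| Lost | k | Completer bias (points) | One-sided error (nominal 0.025) |
|---|---|---|---|
| 5 or 7 | 0 (random) | 0 | 0.02–0.03 |
| 5 | 0.5 | +0.2 to +0.3 | 0.05–0.07 |
| 5 | 1 | +0.4 to +0.6 | 0.08–0.13 |
| 7 | 0.5 | +0.34 to +0.49 | 0.06–0.09 |
| 7 | 1 | +0.58 to +0.83 | 0.11–0.18 |

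Against the planned gain of 3.2, this runs from 0.2/3.2 = 6% to 0.83/3.2 = 26%.

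**An estimate that keeps lost subjects.** Regress y on x in the completers and evaluate the line at the week-13 mean of all 20: estimate = ȳ(completers) + b[x̄(all) − x̄(completers)]. Its variance is s²{1/m + [x̄(all) − x̄(completers)]²/Sxx} + b²·s²(x)/20 on m − 2 df, with m completers. In the same simulations its bias was within 0.02 and its one-sided error 0.020 to 0.029. Under random loss of 7 with a true change of 3.2, power was 0.97 to 0.98, against 0.95 for the paired t-test.

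**BBT.** The documents give no SD, so only SD units are possible. With 7 lost, k from 0.5 to 1 and normal scores, completer bias was 0.12 to 0.21 SD if week 22 is without the orthosis, and 0.12 to 0.25 SD if with it. The second range also assumes that half the true-change variance is an immediate step when the orthosis is put on.

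**The case against.** The strongest reply is that the harm is hypothetical, and much of that stands. A reader might infer from the competence requirement before home use that poor responders leave at week 13. The documents do not support this: a caregiver may meet the checklist, Item 13 lets the number of training sessions be increased, and no text describes withdrawal for failing the checklist. The withdrawal causes that Item 40 describes in detail are shoulder and skin problems. Neither k nor the loss rate comes from the plan, and k = 1 is strong: a subject 1 SD below the mean carries exp(2) = 7.4 times the loss weight of one 1 SD above.

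Nor do the documents support saying that attrition leaves the trial underpowered at the planned effect, or that the intermediate scores go unused; they serve the secondary analyses. Those analyses, as described, supply no inferential protection for the two primary tests.

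One might also want a primary model with all visits and three random terms (intercept, change to week 13, change after it). For 20 subjects that is too much: its simulated one-sided error reached 0.048, and singular or near-singular fits were common. This argues for a smaller model, not for keeping a completers-only test.

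**Conclusion.** The point holds as a conditional weakness that should be fixed. The text settles that both primary comparisons lose every subject without week 22 and that no rule covers them. Random loss does little harm. Under the stated assumptions, loss that follows the week-13 change biases the Fugl-Meyer result upward by about 0.2 to 0.6 points with 5 lost and 0.3 to 0.8 with 7 lost, with one-sided error of about 0.05 to 0.13 and 0.06 to 0.18 against 0.025.

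These figures rest on reading Fugl-Meyer as the therapeutic measure, on the inferred one-sided 0.025, on the assumed measurement SD and loss mechanism, and on normal scores. The proposed estimate was checked in its regression form, not as a fitted REML model. The BBT sizes are weaker still: BBT is a count, entry requires only 1/5 strength, and scores without the orthosis may cluster near zero, which was not simulated.

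**What to change.** 1. Fugl-Meyer: name it as the primary therapeutic measure. Estimate the week-22 minus week-1 change from no-orthosis scores with a likelihood-based repeated-measures model on weeks 1, 13 and 22, with visit as a category, unstructured covariance, REML and small-sample degrees of freedom, keeping every enrolled subject. State the sidedness and the adjusted alpha.
2. Report the completers' paired t-test alongside. An all-visits model with three random terms may be a supporting analysis, with a stated fallback if the fit is singular.
3. BBT: first state whether the week-22 score is with or without the orthosis, then use the matching model and check for floor effects.
4. Add a stepped sensitivity analysis: lower the predicted week-22 Fugl-Meyer change of lost subjects by 0 to 3.2 points and report where the conclusion changes. With 7 of 20 lost, the full step lowers the estimate by 3.2 × 7/20 = 1.12 points. The team sets the BBT range.

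The cost is analysis wording, a little more modelling and one decision on the BBT condition that any BBT test needs. No visits or data are added.

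The model does not correct for loss driven by unobserved response or for loss before week 13; only step 4 addresses these. When 7 were lost right after week 5 according to true response, simulated completer bias was +0.32 to +0.83. Such subjects give the three-visit model only a baseline, so it should do little better. The shift that cancels this is bias × 20/7, or 0.9 to 2.4 points, inside the proposed range.
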